1.2 Primary Objective

The primary objective of this study was to determine if participants with mild to moderately-severe SNHLs find an improvement in streaming sound quality under the novel coupling method (state 1) when compared to the novel coupling method (state 2). Additionally, streaming sound quality of the novel coupling method was compared to traditional open and vented domes.

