2.3 Determination of Sample Size

Sample size was estimated based on a previous version of the study in which the primary outcome was speech in noise recognition. Sample size was estimated using GPower software, for repeated measures ANOVA (Faul et al., 2007; Faul et al., 2009). Past studies in this area have typically used about 20 participants. It should be noted that as a post-market exploration study, a formal sample size estimation for the sound quality evaluation is not mandatory.

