2.5.2 Primary Endpoint Analysis

Sound quality ratings were analyzed using ratings on a scale from 1-100. Ratings were transformed to rationalized arcsine units (Studebaker, 1985). Transformed scores were inspected for normality by visual inspection of histogram data, and protected against departures from sphericity using Greenhouse-Geisser corrections to degrees of freedom. Scores were analyzed using a 3x4 repeated measures analysis of

variance (RM-ANOVA) with stimulus (classical, pop, speech) and condition (state 1, state 2, open dome, closed dome) as the within-subjects factors. Significant effects were located using pairwise comparisons with Bonferroni corrections.

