2.5.3 Secondary Endpoint Analysis

Situational preference data were analyzed using a 2x2x2 RM-ANOVA with condition (state 1, state 2), microphone state (on vs. off), and stimulus (music, speech) as within-subjects factors. Data and analysis followed the same treatment procedures as for the sound quality data. A separate RM-ANOVA was run for when participants were focusing on the stream and for focusing on the external environment. Planned contrasts included: comparison of conditions and or microphone states across stimuli, and comparison of conditions and or microphone states within each stimulus. Comparisons between stimuli were not of interest.

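### Holm's step-down procedure would keep the familywise guarantee of the planned Bonferroni follow-up comparisons and recover a modest amount of power

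*Combined protocol and SAP*

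**What the plan says.** Section 2.5.2 plans a 3x4 repeated-measures ANOVA on the transformed sound quality ratings, with three stimuli and four coupling conditions: "condition (state 1, state 2, open dome, closed dome) as the within-subjects factors". Follow-up is described in one sentence: "Significant effects were located using pairwise comparisons with Bonferroni corrections". No step-down rule is mentioned, so the plain reading is single-step Bonferroni, with every p-value compared with alpha/m. Neither alpha nor the set of comparisons over which the correction runs is stated.

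Section 2.5.3 extends this to situational preference: "Data and analysis followed the same treatment procedures as for the sound quality data". It also lists planned contrasts, without numbering them.

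Section 1.2 puts State 1 versus State 2 first and adds that "streaming sound quality of the novel coupling method was compared to traditional open and vented domes". The primary objective therefore involves several pairwise comparisons.

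On size, section 2.3 gives no planned N for the current outcomes. It says "Past studies in this area have typically used about 20 participants" and that "a formal sample size estimation for the sound quality evaluation is not mandatory". Section 1.1 calls the study exploratory.

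**The concern.** Bonferroni and Holm both hold the familywise error rate at or below alpha under any dependence between the tests. Holm rejects every hypothesis that Bonferroni rejects, and sometimes more. This is a mathematical property and does not depend on N, effect size or the number of comparisons. When the purpose is only to test, single-step Bonferroni therefore gives up some power without buying a stronger guarantee.

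At stake is the power to find second and later differences within a set. In this study that means mainly the comparisons of the novel coupling with the domes, and the planned contrasts on situational preference. It applies whichever set of comparisons is chosen.

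**Working it through.** The documents contain no power or error figure to reproduce, so the check has an exact part and a part that rests on assumptions.

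**Inputs from the documents.** Four conditions (2.5.2) give 4 × 3 / 2 = 6 pairs. Two novel states against two domes (1.2) give 2 × 2 = 4 pairs. The dome that 2.5.2 calls closed is taken to be the vented dome of 1.2.

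**Assumptions.** Familywise 0.05, two-sided. n = 20, borrowed from the remark on past studies in 2.3, with a range of 16 to 24. Normal data with equal variances and equal correlations. Effects are in units of the SD of the paired difference. The requirement of a significant ANOVA effect was not simulated.

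**Thresholds.** Bonferroni compares every p-value with alpha/m. Holm compares the i-th smallest with alpha/(m − i + 1) and stops at the first failure.

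- m = 6, Bonferroni: 0.05/6 = 0.00833 for all six.
- m = 6, Holm: 0.00833, 0.0100, 0.0125, 0.0167, 0.025, 0.05.

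The first threshold is the same under both, so the chance of at least one rejection is identical. Every later Holm threshold is larger, so Holm cannot reject less.

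**Simulation, six pairs.** Paired t-tests, 10,000 to 20,000 trials per scenario, n = 20, two conditions better than the other two by the stated amount (four true differences, two null pairs):

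| True difference (SD) | Power per true pair, Bonferroni | Holm | Gain (points) | Trials with identical decisions |
|---|---|---|---|---|
| 0.3 | 7.9% | 8.5% | about 1 | 98% |
| 0.5 | 27.5% | 30.6% | about 3 | 89% |
| 0.8 | 73% | 79% | about 6 | 77% |
| 1.0 | – | – | about 3 | – |

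At 0.8 SD, the chance of finding all four true differences is 40% with Bonferroni and 55% with Holm. The chance of finding at least one is 96.7% with both. Familywise error is 1.6% and 3.3%. With no true difference anywhere, it is 4.4% with both. In no trial did Bonferroni reject a pair that Holm did not.

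**Other N, same pattern at 0.8 SD.** All four found: 21.9% versus 34.4% at n = 16, and 58.3% versus 71.7% at n = 24.

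**Other pattern.** If only one condition is better by 0.8 SD (n = 20), power per true pair goes from 72.6% to 76.2%, a gain of 3.6 points. Familywise error goes from 2.1% to 3.5%.

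**Four novel-versus-dome pairs.** If State 1 versus State 2 is tested alone, m = 1 and the two procedures coincide. For the remaining four pairs, with the two-versus-two pattern at 0.8 SD, power per true pair is 78% versus 81%, and both true differences are found in 61% versus 67% of trials. Familywise error is 2.5% versus 4.0%.

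**Secondary contrasts.** No simulation was run for these. The ordering of the two procedures still holds, but the size of the gain is unknown.

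**The case against.** The strongest reply is that Bonferroni is valid, standard and conservative, creates no false claim, and is a reasonable choice in an exploratory study. That stands. A reader might infer that 2.5.2 contains an error or that its results would be unreliable; nothing in the documents supports that.

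A reader might also infer that real coupling differences were missed. The documents give no N, alpha, SD, effect size or result, so one can say only that differences can be missed. Nor do they say that the design expects two more closed and two more open fittings. Section 1.1 says only that the novel method aims to draw on both types of fitting, and no section states which state behaves like which dome. The two-versus-two pattern is an assumption of the calculation.

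The 40% versus 55% contrast should not be the headline, because no stated objective needs all four differences to be significant together. At small effects the two procedures nearly always agree.

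Holm is not quite without a price. Its actual familywise error is higher when some differences are real, although within 5%. Bonferroni also pairs with simple simultaneous confidence intervals and Holm does not, but the plan mentions none.

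Finally, the undefined set of comparisons can matter more. Treating the six pairs within three stimuli as one set gives 6 × 3 = 18 comparisons and a Bonferroni threshold of 0.05/18 = 0.0028. With one condition better by 0.8 SD and n = 20, average Bonferroni power falls from 72.6% to 56.5%, and Holm brings it back only to 61.3%. That is a separate point; it limits the importance of this one but does not remove it.

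**Conclusion.** The point holds as a modest efficiency improvement. That Holm keeps the same guaranteed error rate and never rejects less is certain. The size of the gain is conditional: about 1 to 6 points per true pair for differences of 0.3 to 1.0 SD, given n = 20, two-sided 0.05, six pairs and two conditions better than the other two. The gain is about 3 points for the four novel-versus-dome pairs at 0.8 SD, and nil for State 1 versus State 2 if that comparison is tested alone. The chance of at least one rejection does not change.

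**What to change.** In section 2.5.2, replace 'Bonferroni corrections' with 'Holm step-down adjusted p-values (familywise 0.05 within each set of comparisons)'. In section 2.5.3, state that the planned contrasts use the same procedure. The new wording takes effect only once each set of comparisons is listed, so the sets should be named at the same time.

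The cost is a sentence in each section. Holm uses the same unadjusted p-values and is a standard software option; no new data are needed. The document is largely written in the past tense. If the analysis has already been done, changing to a less conservative rule would be a post hoc change. In that case, keep the Bonferroni results as planned and report the Holm-adjusted p-values beside them, labelled post hoc.

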2.5.3 Secondary Endpoint Analysis

Situational preference data were analyzed using a 2x2x2 RM-ANOVA with condition (state 1, state 2), microphone state (on vs. off), and stimulus (music, speech) as within-subjects factors. Data and analysis followed the same treatment procedures as for the sound quality data. A separate RM-ANOVA was run for when participants were focusing on the stream and for focusing on the external environment. Planned contrasts included: comparison of conditions and or microphone states across stimuli, and comparison of conditions and or microphone states within each stimulus. Comparisons between stimuli were not of interest.

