Study Protocol and Statistical Analysis Plan

Lab Evaluation of Novel Hearing Aid Coupling Method - ID# 1082

January 30, 2024

NCT05377359

Lab Evaluation of Novel Hearing Aid Coupling Method - ID# 1082

1 Objectives and hypotheses of the clinical investigation

1.1 Purpose of the clinical investigation claims for clinical performance, effectiveness or safety of the investigational device that are to be verified

The study was an exploratory study in which we evaluated a novel coupling method that allows us to take advantage of both open and closed fittings in a single solution and compared this to traditional coupling methods. The various coupling methods were evaluated using two outcome measures: streaming sound quality and situational preference.

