1.3 Secondary Objectives

The secondary objective of this study was to determine how overall preference ratings for streamed stimuli in realistic noise changes when using novel coupling methods while in different states and while the hearing aid mic is on and off.

2 Design of the clinical investigation

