2.1 General

2.1.1 Design Type

This study was a single-blinded, single group interventional study where stimulus presentation order was randomized between participants. All participants were subject to each test condition (cross-over). There was no control group. Participants and investigators were always blinded to the programs that were being rated during testing.

The table below indicates the various programs that each participant evaluated.

Primary Objective	Novel Coupling Method – State 1
	Novel Coupling Method – State 2
	Open Domes
	Vented Domes
Secondary Objective	Novel Coupling Method – State 1 – Mic Off
	Novel Coupling Method – State 1 – Mic On
	Novel Coupling Method – State 2 – Mic Off
	Novel Coupling Method – State 2 – Mic On

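### Does analysing situational preference separately for each listening focus, with no contrast between the two, leave the secondary analysis short of what it must show?

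*Combined protocol and SAP*

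**What the plan says.** Section 1.1 names two outcome measures, "streaming sound quality and situational preference". The secondary objective in section 1.3 concerns the second of these: "to determine how overall preference ratings for streamed stimuli in realistic noise changes when using novel coupling methods while in different states", and also with the hearing aid microphone on and off. Listening focus is not mentioned there.

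Section 2.5.3 specifies a "2x2x2 RM-ANOVA with condition (state 1, state 2), microphone state (on vs. off), and stimulus (music, speech) as within-subjects factors". Focus is handled by fitting the model twice: "A separate RM-ANOVA was run for when participants were focusing on the stream and for focusing on the external environment". The comparisons to be drawn from each model are then listed: "Planned contrasts included: comparison of conditions and or microphone states across stimuli, and comparison of conditions and or microphone states within each stimulus". One kind of comparison is set aside: "Comparisons between stimuli were not of interest". Comparison between foci is neither listed nor excluded.

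The design is within-subject (section 2.1.1): "All participants were subject to each test condition (cross-over"). The table of programs in that section lists states and microphone settings for the secondary objective, but not focus.

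**The concern.** An outcome called situational preference, rated under two listening foci, invites the question whether the preferred state or microphone setting changes with the situation. With focus split over two models, neither model can yield a focus-by-state or focus-by-microphone contrast, and the plan supplies none from elsewhere.

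Results from two parallel analyses are often read side by side. If state were significant for the stream and not for the environment, a reader might conclude that the effect depends on focus. That inference is unsound, because two tests of the same true effect often fall on opposite sides of 0.05 by chance. At stake would be a false claim that preference depends on the situation. The plan neither tests for such dependence nor says that conclusions stay within each focus.

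**Working it through.** **Step 1: the question against the analysis.**

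| Element | Secondary objective (section 1.3) | Analysis (section 2.5.3) |
|---|---|---|
| Coupling state | asked | factor in each model, with planned contrasts |
| Microphone on or off | asked | factor in each model, with planned contrasts |
| Stimulus | streamed stimuli, no comparison asked | factor; comparison between stimuli declared of no interest |
| Listening focus | not named | separate model for each focus; no comparison planned |

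Everything the objective asks about is tested. The one thing not tested, a difference between foci, is not asked about in section 1.3, in the purpose statement of section 1.1 or in section 2.5.3. Naming an outcome situational preference says what is rated. It does not promise a test between situations.

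**Step 2: how often would two separate results disagree?** The documents give no sample size, significance level, effect size or correlation for this endpoint. Section 2.3 says only that "Past studies in this area have typically used about 20 participants". The assumptions are therefore n = 20, two-sided 0.05, the same true standardised paired effect dz under both foci, and a correlation rho between the two state differences. Each state effect has one degree of freedom, so it is equivalent to a paired t-test.

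If the two differences are independent (rho = 0) and each test has power p, the chance that exactly one is significant is 2p(1 − p):

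- dz = 0.5: p = 0.565, so 2 × 0.565 × 0.435 = 0.49.
- dz = 0.66: p = 0.799, so 2 × 0.799 × 0.201 = 0.32.
- dz = 0.8: p = 0.924, so 2 × 0.924 × 0.076 = 0.14.

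Simulation with 100,000 studies per cell agrees at rho = 0 and extends to positive correlation:

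| dz | rho 0 | rho 0.3 | rho 0.5 | rho 0.7 |
|---|---|---|---|---|
| 0.2 | 0.234 | 0.206 | 0.177 | 0.142 |
| 0.5 | 0.490 | 0.406 | 0.337 | 0.261 |
| 0.8 | 0.140 | 0.126 | 0.111 | 0.089 |
| 1.0 | 0.023 | 0.022 | 0.020 | 0.017 |

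A direct interaction test on the difference of differences rejects in 4.9% to 5.1% of studies in all these cells. Over dz 0.2 to 1.0, disagreement spans 11% to 50% at n = 12 and 0.1% to 50% at n = 30.

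**Step 3: what these figures measure.** They are the error rate of one particular rule: declare a difference by focus when exactly one of the two tests is significant. Section 2.5.3 contains no such rule. Its contrasts concern state and microphone setting inside each model. A test of state under one focus has the same type I error whether or not a second model is fitted for the other focus. The figures are sound arithmetic about a step that the plan does not take.

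**Step 4: what an added contrast would deliver.** The 95% half-width of the focus-by-state double difference, in SDs of the state difference, is t(0.975, 19) × √(2 − 2rho) / √20. This is 0.662, 0.554, 0.468 and 0.363 for rho = 0, 0.3, 0.5 and 0.7. At this assumed size the contrast would be imprecise, and it would serve a question outside the stated objective.

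**The case for a change.** The best case for the concern is that it need not claim the separate models are wrong. Ratings are collected under two foci and the results will appear side by side, so comparison is natural. The plan shows that it can rule a comparison out, since it does so for stimuli, yet it is silent on foci. Being exploratory does not turn a pair of p-values into evidence of a difference. The cure is cheap: one more model or one sentence, on data already collected.

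The statistical principle stands. Any statement that the effect differs by focus needs a direct test, and the plan has none. The simulated figures also stand under their assumptions.

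The step from there to a defect does not. The exclusion for stimuli has a reason that focus lacks: stimulus is a factor in each model, so comparisons between stimuli would otherwise arise from the fit. Focus is in neither model, so there is nothing to exclude. Separate models with contrasts limited to state and microphone setting already define a within-focus analysis, and a limiting sentence would only repeat this. The split is also reasonable in itself, since attending to the stream and attending to the surroundings are different listening tasks, and the preferred state in each is of interest.

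The added contrasts would raise questions of their own. Two tests at 5% each give up to 2 × 5% = 10% for any false claim unless they come under the Bonferroni correction of section 2.5.2. Pairing by participant across foci is plausible from section 2.1.1 but not stated for focus.

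**Conclusion.** The concern does not hold. Followed as written, section 2.5.3 gives valid results on state and microphone setting within each listening focus, which is what section 1.3 asks for. No between-focus claim is planned, so the absence of a between-focus test leaves no stated question unanswered and makes no planned result wrong.

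The disagreement rates, 26% to 49% at dz = 0.5 and about 2% at dz = 1.0 with 20 participants, rest on an assumed sample size, significance level, effect size and correlation. They apply only if someone compares the two p-values. They are a caution for reading the results, not a measure of error in the plan. The conclusion would change if a section stated an aim or a conclusion about differences between foci; none does. Adding a focus contrast is an optional extension of an exploratory secondary analysis.
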